**Brief Intervention for Justice-Involved Substance Users:
Harnessing Mechanisms of Change**

NCT03308877

04/01/2017

D.7. Data Analysis. A baseline check of randomness will be conducted for each variable collected. Categorical variables will be analyzed using chi-square tests; continuous variables with ANOVAs. To assess Hypothesis 1 continuous outcomes, Analysis of Covariance will be used. The effects of BMI+SC on commitment to change, self-regulation, and substance use will be assessed immediately following intervention. Longer term substance use effects will be examined at 6-month follow-up. For substance use toxicology results, logistic regression will be used. In all instances, alpha = .05; covariates will include gender, race, age, and the outcome baseline score of interest as well as any other variables found to differ at baseline. Additionally, effect sizes will be examined using marginal means.⁷¹ Structural equation modeling (SEM) will be used to test the hypothesis that the effect of BMI+SC on substance use will be mediated by increases in commitment to change and self-regulation (Figure 2).⁷² *Substance use status* at six month follow-up is the key outcome of interest. We hypothesize that effects on six month substance use are mediated, in part, by BMI+SC effects on commitment to change and self-regulation. Substance use status will be measured using two indicators, percent days abstinent and the urine screen result. *Commitment to Change* will be measured using two indicators at each time point, the Readiness Ruler and the CLEAR change talk score at both baseline and immediate post. Two indicators will also be used to assess *Self-Regulation* at baseline and immediate post: Self-Regulation Questionnaire scores and Balloon Analog Risk Task scores. Additionally, demographic variables will be statistically controlled for in the model (gender, age, race, ethnicity). The MPLUS statistical package⁷³ will be used for SEMs. To provide a metric for each latent construct and to identify the model, the first construct loading for each latent variable will be set at 1.0. A two-step approach examining the model will be undertaken.⁷⁴ First, using confirmatory factor analytic techniques, a test of the proposed measurement model will be conducted and any needed modifications to this model, including testing for measurement invariance over time, will be undertaken prior to examining model fit. The second step involves an examination of the structural portion of the model. The model suggests that BMI effects on substance use are not only direct, but also indirect, mediated by effects on commitment to change and self-regulation. Baseline substance use status, commitment to change, and self-regulation will be controlled for, aiding precision in detecting treatment effects. Fit of the model will be assessed using a chi-square statistic, as well as the more approximate fit indices of the root mean square error of approximation (RMSEA),⁷⁵ the comparative fit index (CFI),⁷⁶ and the standardized root mean square residual (SRMR). Using various cutoffs for fit assessment helps to minimize Type I and Type II errors.⁷⁷ Recommendations that adequate fitting models have $CFI > .95$, $RMSEA < .06$, and $SRMR < .08$ will be adopted here. BMI indirect effects on 6 month substance use will be tested using the bias-corrected confidence limits.⁷⁸ Significance will be assessed by whether or not the 95% confidence limits contain zero. The bias corrected approach has been shown to provide the most accurate confidence limits and greatest statistical power when compared with other existing approaches for detecting mediation.⁷⁸ Multi-group structural equation modeling will be used to test moderated mediation. Two groups (high vs. low/moderate on affective psychopathy) will be compared. We will isolate differences across models by first examining if measurement parameters are equal across groups. Model differences across groups will be tested using the chi-square difference test. Next, we will test for structural differences across groups, examining regression parameter estimates for equality, followed by an examination of latent variables' variances and means across the groups. Such moderated-mediation will allow for isolation of BMI effects on latent variable means, controlling for process differences across the groups. Four exploratory analyses will also be conducted. The first will examine longitudinal change in substance abuse using growth curve analyses. Substance use is measured at baseline, 4 times during the intervention period, and at 6-month follow-up (6 time points). Time will be modeled so that the intercept reflects baseline status and subsequent time points will be modeled as weeks from baseline. Both linear and curvilinear (quadratic) change

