
will be examined using the same covariates as previously mentioned. Here, we are interested in the time by condition interaction term, addressing whether the trajectory of substance use differs across the BMI+SC and SC groups. Second, we will determine whether BMI+SC had an effect on violent recidivism using logistic regression. We will also use the structural equation models above to examine mediational and moderated mediation effects of BMI on violent recidivism. Finally, we will also examine the moderated mediation models across gender and race (white vs. black) to determine if mean and/or process differences exist for males and females as well as for White and Black participants. (Numbers of other races/ethnicities are likely to be too low for separate analysis).

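### The planned test of moderated mediation compares individual paths and latent means across psychopathy groups, but never BMI's indirect effect, and no result is named that would count as moderated mediation

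*SAP*

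**What the plan says.** SAP D.7 first describes a mediation model in which BMI+SC affects six-month substance use directly and through commitment to change and self-regulation. The indirect effects are tested with bias-corrected 95% limits and judged by whether those limits contain zero.

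The moderation part follows: "Multi-group structural equation modeling will be used to test moderated mediation". "Two groups (high vs. low/moderate on affective psychopathy) will be compared". The steps are:

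1. Measurement: "We will isolate differences across models by first examining if measurement parameters are equal across groups". The statistic is given here: "Model differences across groups will be tested using the chi-square difference test".
2. Structure: "Next, we will test for structural differences across groups, examining regression parameter estimates for equality".
3. Distributions: "followed by an examination of latent variables' variances and means across the groups".

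The paragraph concludes: "Such moderated-mediation will allow for isolation of BMI effects on latent variable means, controlling for process differences across the groups".

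The same models are then used for violent recidivism, and the SAP adds that "we will also examine the moderated mediation models across gender and race (white vs. black"). These further uses fall among the exploratory analyses. The psychopathy comparison is described before them.

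No sentence defines an indirect effect within each psychopathy group, contrasts the two, or says which result would count as moderated mediation. SAP D.7.1 gives power for overall model fit only, with none for a group difference in paths or indirect effects.

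**The concern.** With a the path from BMI to the mediator and b the path from mediator to substance use, the indirect effect is a × b. Moderated mediation means that a × b differs between the high and the low/moderate psychopathy groups. The SAP judges mediation overall by this product and its interval, but drops the product when it compares groups.

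Testing paths for equality addresses another hypothesis. Paths can differ while the products are the same: b may differ when BMI moves the mediator in neither group, a and b may differ in opposite directions, or only the direct path may differ. A significant chi-square difference could then be reported as BMI working through a different mechanism in people high in psychopathy although the mediated effect is the same in both groups.

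The sentence on latent means adds a second uncertainty. Under Protocol D.3 and D.4.3, participants are randomised within pairs matched on psychopathy group. A BMI contrast within a psychopathy group is therefore randomised. A latent-mean difference between psychopathy groups is not, and is not a BMI effect.

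**Working it through.** **The plan's own figures.** The only SEM power figures in SAP D.7.1 concern RMSEA. With noncentrality λ = (N − 1) × df × RMSEA², N = 416 and 94 df:

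- RMSEA .08: 415 × 94 × .0064 = 249.7
- RMSEA .05: 415 × 94 × .0025 = 97.5
- RMSEA .01: 415 × 94 × .0001 = 3.9

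At alpha .05 the power is 0.9998 (null .08, true .05) and 0.9996 (null .05, true .01). At N = 300 it is 0.996 and 0.986. The plan's figures (above .95, .99, and above .90 at N = 300) hold, but they say nothing about detecting a group difference in indirect effects.

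**Inputs.** From the SAP: N = 416, two groups, alpha .05, and a direct path in the model. Assumed, because the documents do not give them: the path values, the group split (208/208 or 104/312), two-sided tests, and one observed mediator in place of two latent ones.

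**Tests compared.**

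- Path equality: the sum of (difference in path)² ÷ (sum of the two variances), over a, b and the direct path (3 df) or over a and b (2 df). This Wald test is asymptotically equivalent to the chi-square difference test.
- Direct contrast: the 95% Monte Carlo interval for a₁b₁ − a₂b₂, rejecting if it excludes zero.

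**First set:** 3,000 trials per setting, 3 df path test, mediator residual variance 1 and outcome residual variance 1 − b². In the unequal split the first-named group has 104. Cells give rejection at 208/208, then at 104/312.

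| Setting (a × b, group 1 v group 2) | Path test | Direct contrast |
|---|---|---|
| All paths equal, .4 × .3 | 5%, 6% | 4%, 5% |
| Equal products, .2 × .6 v .6 × .2 | 99%, 97% | 5%, 5% |
| Equal products, .24 × .5 v .5 × .24 | 76%, 63% | 5%, 6% |
| Equal products, .3 × .4 v .4 × .3 | 16%, 13% | 5%, 6% |
| Same a and b, direct path 0 v .4 | 38%, 30% | 4%, 5% |
| a = 0 in both, b = .5 v .1 | 96%, 92% | 5%, 5% |
| Products differ, .20 v .04 (.5 × .4 v .2 × .2) | 60%, 45% | 63%, 41% |
| Products differ, .20 v 0 (.5 × .4 v 0 × .4) | 56%, 44% | 67%, 55% |

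With all paths equal, testing a, b and the direct path one at a time at .05 gives at least one rejection in 13% (208/208) or 14% (104/312) of trials.

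**Second set:** 2 df path test, residual variance 1, low/moderate group named first. Cells give 312/104, then 208/208.

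| Setting | Path test | Direct contrast |
|---|---|---|
| a = 0 in both, b = .2 v .5 (both products 0) | 64%, 78% | 4% to 6% |
| .5 × .25 v .25 × .5 (both products .125) | 57%, 73% | 4% to 6% |
| .5 × .4 v .1 × .2 (.20 v .02) | 59%, 71% | 69%, 73% |
| a = .3 in both, b = .2 v .5 (.06 v .15) | 63%, 78% | 12%, 18% |

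**A stricter rule.** Suppose a claim needs both unequal paths and an indirect-effect interval excluding zero in at least one group. In the first row of the second table the rate falls to about 8%. In the second row, where both indirect effects are real and equal, it stays at 56% (312/104).

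**The case against.** A reader might infer that the SAP would declare moderated mediation at the rates above. The documents do not support that. No sentence says that a path difference alone counts, and the SAP does test BMI's indirect effect by its interval. If that test were applied within groups and required as well, the case in which BMI moves the mediator in neither group would largely disappear (about 8%). Applying it within groups is itself an interpretation, since the SAP does not say so.

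Nor are the rejections in the equal-product settings false in every sense. With .5 × .25 v .25 × .5, BMI's effect on the mediator does differ, and a statement that this path differs would be correct. It becomes an error only when called a difference in the mediated effect. Exactly equal products are also a special case.

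It is tempting to call the direct contrast more powerful. It is ahead at 312/104 (69% v 59%) but hardly at 208/208 (73% v 71%), and far behind when only b differs. Path equality therefore carries information worth keeping.

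The sentence on latent means might be read as an error to delete. It may instead mean the BMI effect on each latent mean within a psychopathy group, which is a randomised contrast. It is ambiguous rather than wrong.

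Finally, a reader might take this as the trial's central question and hence a fatal fault. The documents do not rank it so. The SAP names six-month substance use status as the key outcome, and the Hypothesis 1 covariance and logistic analyses are untouched.

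What stands is that no between-group contrast of the indirect effect is planned and no criterion is stated. The Benjamini-Hochberg adjustment in D.7.1 does not fill this gap: it deals with the number of tests, not with which hypothesis is tested.

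**Conclusion.** The concern holds as a gap in the method and in the decision rule. The steps listed for moderated mediation do not test whether BMI's indirect effect differs by affective psychopathy, and a path difference alone cannot support that claim. When the indirect effects were equal but paths differed, the joint 3 df path test rejected in 13% to 99% of simulated trials, and the direct contrast in about 5%. These are error rates of the natural reading of the steps, not of a rule the SAP states.

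The size depends on assumed path values, an assumed group split and a single observed mediator. It is small for modest path differences (13% to 16% for .3 × .4 v .4 × .3). The direction follows from the algebra and does not depend on these assumptions. Severity: should-fix.

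**What to change.** - In Mplus, already the named package, define the indirect effect through each mediator in each psychopathy group, and the between-group difference. Report the difference with its bootstrap 95% limits.
- State that a claim of moderated mediation, meaning a differing indirect effect, rests on that interval.
- Keep the path-equality tests alongside it, reported as differences in specific paths and not as moderated mediation.
- Clarify that the BMI effects on latent means are BMI contrasts within each psychopathy group, because a comparison of means across psychopathy groups is not randomised.
- Apply the same rules to the exploratory gender, race and violent recidivism models.

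The cost is SAP wording and a few lines of model code, with no new data or recruitment. The downside is power. With a = .3 in both groups and b = .2 v .5, the contrast detects a real difference in indirect effects in about 12% to 18% of trials, while the path test detects the path difference in 63% to 78%. The SAP should say that a non-significant contrast is not evidence of no moderation.

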D.4.3. Sessions 2 and 3: Baseline Assessments A and B. Participants who qualify will complete two baseline assessment sessions, scheduled within one week of each other, to gather thorough multi-method data while minimizing subject burden. For *Baseline A* we will administer the Timeline Followback Interview (TLFB)⁵⁷ to measure drug and alcohol use frequency in the past 90 days and the 125-item PDSQ⁵¹ to screen for mental disorders. We will then administer a standard psychopathy interview - a semi-structured interview designed to gather information regarding education, relationships, family life, and criminal, medical, and work history. The Psychopathy Checklist-Revised (PCL-R)³¹ will be scored based on this interview and a review of the participant's MCPS file. Following the interview, all participants will receive the names and numbers of drug and alcohol treatment providers, and will be paid \$20 for their time. *Baseline B* will be primarily for the initial assessment of mediators of behavioral change. First, we will administer the Self-Regulation Questionnaire⁵⁸ and the Readiness Ruler.⁵⁹ Participants will then complete a behavioral task – the Balloon Analogue Risk Task (BART)⁶⁰ as a second method of assessing self-regulation. Finally, we will gather extensive information on nonstudy treatment utilization using the Economic Form-90,⁶¹ a valid interview that obtains information about recent health services use. This will include treatment type (e.g., medication vs. psychosocial, individual vs. group, and substance use vs. mental health). This information will be supplemented with information on treatment modality collected from area substance use treatment centers. For example, of the four service providers contacted by the P.I. since the initial submission, all provided data on modality (12-step/abstinence based vs. cognitive behavioral or integrative). Following Baseline B, participants will be randomized in matched pairs – based on affective psychopathy group – to BMI+SC or SC.

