enhance the efficacy of the intervention and perhaps broaden its therapeutic effects to more participants. This update involves dropping the use of a decisional balance exercise in order to decrease the amount of time spent talking about positive drug use experiences – a practice that may be detrimental and may elicit cravings.^{63,64} Our BMI manual (Appendix B) includes the following steps: establishing rapport, asking permission to discuss drugs and providing feedback regarding the drug use assessment, exploring personal consequences of drug use, eliciting the gap between real and desired quality of life, and discussing readiness to change. The therapist then negotiates a written action plan, during which the participant is supported with empathy, verbal reinforcement, information about drug abuse and treatment providers, and a referral for treatment.¹⁵ Continuing care is important for substance users⁶⁵ and data show that having more than one BMI session significantly enhances outcomes,⁶⁶ thus we will include brief (20-30 minutes), flexible, follow-up intervention sessions (Weeks 2, 4, and 6). Each follow-up session will be preceded by an assessment of substance use since the last session by personnel who are blind to psychopathy and treatment status. The Week 6 follow-up will also include readministrations of the BART and Self-Regulation Questionnaire (mediators) to assess change in self-regulation since baseline. Individuals in the BMI+SC and SC conditions will receive the same number of assessments and the same compensation (\$50) for assessment time. Individuals in both the BMI+SC and SC conditions will be assessed for substance use and treatment contacts at Weeks 2,4 and 6 and again at 6 months.

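### The exploratory growth curve, read through its time-by-condition term alone, does not separate a lasting effect from one that fades after Week 6; a slope change at Week 6 would.

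*SAP*

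**What the plan says.** SAP D.7 introduces the growth curve as the first of a set of secondary looks: "Four exploratory analyses will also be conducted". It describes the data as follows: "Substance use is measured at baseline, 4 times during the intervention period, and at 6-month follow-up (6 time points". All visits share one time axis: "Time will be modeled so that the intercept reflects baseline status and subsequent time points will be modeled as weeks from baseline". The shapes allowed are "Both linear and curvilinear (quadratic) change", and the result to be read is stated as: "we are interested in the time by condition interaction term, addressing whether the trajectory of substance use differs" between arms. The SAP gives no change of slope at the end of the intervention, no categorical time, no contrast between 6 months and Week 6, and no rule for matching recall windows.

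The Protocol supplies the timing. D.3 places one session as near to baseline as possible and the others at 2, 4 and 6 weeks, with substance use assessed in both groups. In D.4.3 the baseline interview is used "to measure drug and alcohol use frequency in the past 90 days". D.4.4 says of the follow-up sessions: "Each follow-up session will be preceded by an assessment of substance use since the last session". The same section says that both arms "will be assessed for substance use and treatment contacts at Weeks 2,4 and 6 and again at 6 months". I found no stated recall window for the 6-month visit. D.4.1 refers to a table of measures in Appendix C, which is not among the documents.

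**The concern.** The intervention ends at Week 6, and about 20 weeks then pass without an assessment. If the arms differ at Week 6, the natural next question about trajectory is whether the difference persists. A straight line or a single parabola over 0 to 26 weeks cannot bend at Week 6, and the one late visit largely decides its shape. Anyone reading only the time-by-condition coefficients could then report continuing growth for an effect that had gone, or give the same account of a lasting and a lost effect.

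The points also summarise unequal stretches of time: 90 days at baseline, about two weeks at Weeks 2 to 6, and an unstated period at 6 months. That blurs any change between Week 6 and 6 months.

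**Working it through.** **The plan's own count.** Baseline 1 + intervention period 4 + 6 months 1 = 6. This agrees with Protocol D.3 (near baseline, then Weeks 2, 4 and 6). The list in D.4.4 gives 1 + 3 + 1 = 5.

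**Inputs.** From the documents: visits at Weeks 0, 2, 4, 6 and 6 months, plus a first session near baseline; linear and quadratic time in weeks; recall of 90 days at baseline and since the last session at Weeks 2, 4 and 6. Assumed, because the documents do not say: first session at Week 0.5 with the same since-last-visit recall; 6 months = Week 26; arm difference 0 before baseline, rising linearly to 1 at Week 6, then holding at 1 or fading linearly to 0 at Week 26; 6-month recall between 90 days and 20 weeks. The data are noise-free and the fits are ordinary least squares.

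**Leverage of the 6-month point, linear fit.** For t = 0, 0.5, 2, 4, 6, 26: mean = 38.5/6 = 6.417; Sxx = 732.25 - 6 × 6.417² = 485.2. Leverage = 1/6 + (26 - 6.417)²/485.2 = 0.167 + 0.790 = 0.96. For the quadratic it is 1.00, so that curve passes through the 6-month value.

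**Window averages.** The sessions at 0.5, 2, 4 and 6 weeks record 0.042, 0.208, 0.500 and 0.833. At 6 months a held effect records 1. A fully faded one records (1 + 0)/2 = 0.50 over Weeks 6 to 26. Over the last 90 days (12.86 weeks) it records (12.86/20)/2 = 0.32.

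**Linear slope** = (Σty - 6.417 Σy)/Sxx.

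| Truth after Week 6 | Values used | Calculation | Slope per week |
|---|---|---|---|
| Holds | windowed | (33.44 - 16.58)/485.2 | +0.035 |
| Fades to 0 | point values | (9.375 - 13.368)/485.2 | -0.008 |
| Fades to 0 | 90-day 6-month window | (15.79 - 12.22)/485.2 | +0.007 |
| Fades to 0 | 20-week 6-month window | (20.44 - 13.37)/485.2 | +0.015 |

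The held slope is larger, but the true peak is unknown, so size does not settle the matter. A vanished effect with peak 1 and a 20-week window has the same slope as a lasting effect with peak 0.0146/0.0348 = 0.42.

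**Quadratic.** With windowed values, the fitted change from Week 6 to Week 26 is 20 × b1 + (26² - 6²) × b2 = 20 × b1 + 640 × b2.

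| Truth | b1 | b2 | Fitted Week 26 minus Week 6 | Peak of curve |
|---|---|---|---|---|
| Holds | 0.16631 | -0.004849 | 3.326 - 3.103 = +0.22 | 1.38 near Week 17 |
| Fades, 20-week window | 0.17178 | -0.005794 | 3.436 - 3.708 = -0.27 | 1.23 near Week 15 |
| Fades, 90-day window | 0.17373 | -0.006131 | 3.475 - 3.924 = -0.45 | 1.18 near Week 14 |

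The coefficients share a sign and are close in size, while the contrast built from them changes sign. With point values the contrast is +0.03 (holds) against -0.96 (fades), close to the true 0 and -1.

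**Piecewise model, knot at Week 6.** With point values it recovers 0.00 and -1.00 exactly. With windowed values it gives +0.20 (holds), -0.30 (fades, 20-week) and -0.48 (fades, 90-day). The knot alone therefore does not remove the dilution from recall. With 14-day windows at Week 6 and 6 months, the fitted values run from 0.80 to 1.00 (holds) and from 0.80 to 0.05 (fades). A held effect still seems to grow by 0.20, because use during Weeks 4 to 6 is recorded while the effect is still rising.

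**Cost in precision.** With 208 per arm (half of the SAP's 416), complete data and an assumed equal correlation of 0.5 between visits, the standard error of the Week 26 minus Week 6 contrast is 0.090 SD for the piecewise model and 0.088 SD for the quadratic. Each uses two time terms.

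Dropping the first session, leaving five points, changes little: with the 20-week window the faded slope is +0.012 and the quadratic contrasts are +0.23 and -0.27.

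**The case against.** The strongest reply is that the SAP asks only whether trajectories differ, labels the analysis exploratory, and already compares substance use by ANCOVA both immediately after the intervention and at 6 months. All of that stands. Those two comparisons show whether there is an early effect and whether one is present later. Neither tests the change between them.

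A reader might infer that the growth curve cannot show fading at all. That goes too far. The quadratic's fitted contrast distinguishes the two cases, and the gap is that nobody has planned to compute it. The knot also looks good here partly because the assumed truths bend at Week 6, and its straight line through the gap is no more testable than the parabola.

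A reader might also infer that the unequal windows bias the treatment comparison. The documents do not support that: both arms have the same number of assessments on the same schedule, so the windows blur timing and dilute change but do not by themselves favour an arm at any visit. Nor do the documents say that 6-month recall reaches back to Week 6. The since-last-session wording describes the follow-up sessions, which is why a range is used above.

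Finally, D.4.4's shorter visit list might be read as showing that the SAP's six points are wrong. Protocol D.3 supports four intervention-period assessments in both groups, so this is a wording mismatch.

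**Conclusion.** The point holds in a limited form. As specified, the linear term cannot tell a lasting effect from a fading one, and the quadratic interaction coefficients read alone barely can: 0.166 and -0.0048 for holding, against 0.172 and -0.0058 for full fade with a 20-week window. The peak that the quadratic draws between Week 6 and 6 months is produced by the visit spacing. The 6-month minus Week 6 contrast is informative under either the quadratic or the piecewise model, but it is not planned.

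The sizes rest on assumed effect profiles, visit times, recall windows and correlation, none of which the documents give. The leverage of 0.96 and 1.00 depends only on the visit times. No primary result depends on this analysis, and the two ANCOVAs are untouched, so this is a minor improvement.

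**What to change.** 1. In SAP D.7, replace the single linear/quadratic time-by-condition term with a piecewise model with a knot at Week 6: one interaction slope for Weeks 0 to 6 and one for Week 6 to 6 months. Equivalently, prespecify a test of the change in the arm difference from Week 6 to 6 months. The cost is a few lines of SAP text and little precision. The path between Week 6 and 6 months remains an untested straight line.
2. State the recall window at 6 months. Where day-level data exist, compute percent days abstinent for this analysis over one common window, for example the 14 days before each assessment. The documents name the day-by-day interview only at baseline, so check that follow-up data allow it. Short windows give noisier values.
3. Reconcile the visit list in Protocol D.4.4 with Protocol D.3 and SAP D.7, stating whether substance use is recorded at the first session in both arms.

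### The exploratory growth curve uses baseline substance use as both first outcome and covariate, which distorts its intercept and biases the trajectory test if outcome-related dropout differs by arm

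*SAP*

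**What the plan says.** SAP D.7 sets the general adjustment rule: "covariates will include gender, race, age, and the outcome baseline score of interest as well as any other variables found to differ at baseline". Later in the same section it introduces the exploratory work ("Four exploratory analyses will also be conducted"), the first item of which is a growth curve for substance use. The outcome series starts at baseline: "Substance use is measured at baseline, 4 times during the intervention period, and at 6-month follow-up (6 time points". The time scale is defined so that baseline is the origin: "Time will be modeled so that the intercept reflects baseline status and subsequent time points will be modeled as weeks from baseline". Linear and quadratic change "will be examined using the same covariates as previously mentioned", with no exception for the baseline score. The quantity to be tested is clear: "we are interested in the time by condition interaction term".

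The structural equation text, the other place to which the cross-reference could point, also adjusts for baseline use: "Baseline substance use status, commitment to change, and self-regulation will be controlled for".

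Protocol D.3.1 expects about 25% attrition. SAP D.7.1 specifies pairwise deletion for mean and rate differences, with multiple imputation as a sensitivity analysis. It names no missing-data rule for the growth curve.

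**The concern.** Read together, these sentences put the same number on both sides of one model. At time 0 the baseline score is regressed on itself. The person-level intercept, which the SAP wants to represent baseline status, becomes what is left over once baseline has been removed.

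The consequence that matters is for missing data. A likelihood-based growth model handles a missing 6-month value through the covariance between the observed and missing points. If the double use of baseline distorts that covariance, the implied trajectory of those who drop out is also distorted. The distortion can cancel in the arm comparison, but need not. At stake is the SAP's only analysis of whether the course of substance use differs between BMI+SC and SC over all six measurements.

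**Working it through.** The documents give no power, precision or bias figure for the growth curve, so there is none to reproduce. The check is short algebra followed by simulation.

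**Inputs from the documents.** 536 randomised in matched pairs (Protocol D.3, D.3.1), hence 536/2 = 268 per arm; about 25% attrition; "In all instances, alpha = .05", taken as two-sided because sidedness is not stated; six occasions.

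**Assumed, not in the documents.** Occasions at weeks 0, 0.5, 2, 4, 6 and 26; intercept variance 0.50; residual SD 0.70 (variance 0.49); slope SD 0.25 per 10 weeks; dropout driven by the last observed score; true effect 0 or 0.2 SD at week 26. Baseline variance is 0.50 + 0.49 = 0.99, so results read as SD units. Models are linear with random intercept and slope, fitted by maximum likelihood, 400 trials per scenario.

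**Step 1: the intercept.** At week 0 the baseline score predicts itself with coefficient 1. If intercept and slope are uncorrelated, later scores regress on it with coefficient 0.50/0.99 = 0.505. One main effect has to compromise between the two; the fitted value was 0.61 to 0.64. The random-intercept variance fell from a true 0.50 to 0.09–0.11, a loss of 1 − 0.11/0.50 = 78% to 1 − 0.09/0.50 = 82%. The fixed intercept at the covariate mean stayed at about its true value of 0.

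**Step 2: the time-by-condition estimate at week 26.** Model A has baseline as outcome and covariate (the text as written). Model B has baseline as outcome only. Each bias cell gives the result for true effect 0, then 0.2.

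| Dropout (SC / BMI+SC) | Bias, A | Bias, B | Null rejection, A | Null rejection, B |
|---|---|---|---|---|
| None | 0.004, 0.000 | 0.004, 0.000 | 0.052 | 0.052 |
| Outcome-related, same in both arms (25% / 25%) | −0.002, 0.002 | −0.002, 0.001 | 0.065 | 0.060 |
| Outcome-related in SC only (25% / 17%) | 0.043, 0.042 | 0.000, 0.000 | 0.087 | 0.045 |
| Opposite direction by arm (25% / 26%) | 0.091, 0.092 | −0.002, −0.001 | 0.140 | 0.050 |

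Simulation error is about 0.005 for bias and √(0.05 × 0.95/400) = 0.011 for a rejection rate near 0.05. Relative to an assumed 0.2 SD effect, the last two rows are biases of about 0.042/0.2 = 21% and 0.092/0.2 = 46%. Coverage of Model A in the last row was 0.85 to 0.86.

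**Step 3: consistency of bias and rejection.** With standard errors of 0.102 and 0.104, the null biases are 0.043/0.102 = 0.42 and 0.091/0.104 = 0.875 standard errors. Expected two-sided rejection is Φ(−1.96 + 0.42) + Φ(−1.96 − 0.42) ≈ 0.07, and Φ(−1.085) + Φ(−2.835) ≈ 0.14. The simulated 0.087 and 0.140 agree within simulation error.

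**Step 4: other assumed values.** Take SDs of 20 (intercept), 6 per 10 weeks (slope) and 15 (residual), so that the baseline SD is √(400 + 225) = 25 points. Let 6-month dropout depend on Week 6 use in SC only, n = 536, with no true effect. One dropout model (120 trials) gave bias 0.44 per 10 weeks: 0.44 × 2.6 = 1.14 points, or 1.14/25 = 0.046 SD. Another, with about 25% lost per arm (150 trials), gave 0.26: 0.26 × 2.6 = 0.68 points, or 0.027 SD, with null rejection 0.047 (simulation error about 0.018). A further run with its own assumed variances and dropout strength (120 trials per scenario) gave about 0.03 SD for one-arm and 0.065 SD for opposite-direction dropout, and random-intercept variance falling from about 0.49 to 0.10. The range across all runs is 0.027 to 0.092 SD.

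**Step 5: the two remedies.** Model B had bias between −0.002 and +0.004 SD in all eight scenarios of Step 2, with null rejection 0.045 to 0.060. Keeping baseline as a covariate and starting outcomes after baseline gave bias of at most about 0.018 SD and null rejection 0.045 to 0.052.

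The quadratic form was not simulated.

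**The case against.** A reader might infer that outcome-related dropout by itself biases the trajectory test. The documents do not support that. With the same mechanism in both arms there was no bias; the dropout-outcome relation has to differ by arm, and the documents state only an overall attrition figure. A difference is plausible, since only BMI+SC receives therapist sessions (Protocol D.4.4), but it is not stated.

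A reader might also infer that the intercept loses all connection with baseline, or that the arms will falsely appear unequal at time 0. The first goes too far: the mean intercept at the covariate mean is kept, and the SAP sentence mainly concerns time coding. The second concerns a test that the plan does not propose.

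Three further objections carry weight:

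- The SAP does not say whether covariates predict the intercept only or the slope as well. Adding a baseline-by-time term removed the bias in the SC-only null case of Step 2 (0.001), and cut it from 0.26 to 0.06 per 10 weeks in the second dropout model of Step 4.
- The planned multiple imputation could help. Imputing the 6-month value from earlier scores and arm, then fitting the criticised model, left bias of 0.01 in that same setting. However, SAP D.7.1 neither ties imputation to the growth curve nor specifies the imputation model.
- The cross-reference could be meant to cover demographics only, in which case the problem disappears. Nothing says so, and both covariate descriptions in D.7 include baseline use. A programmer following the text would include it.

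These points limit the consequence. They do not remove the contradiction in the wording.

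**Conclusion.** The defect is real and minor. As written, the growth curve uses baseline substance use twice, which is a stated rule that misspecifies the model and not just a missing detail. With a main-effect covariate, the random intercept and the time-0 arm term no longer describe baseline status; this follows from the specification and needs no dropout assumption. The size of the variance loss, about 80%, does depend on the assumed variances.

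The planned test is unaffected with complete data or with a common dropout mechanism. If the mechanism differs by arm, the bias is roughly 0.03 to 0.09 SD at week 26, and null rejection runs from about 0.05 (no detectable inflation) to 0.14. Those figures rest on assumed covariances, dropout models and a linear curve; none can be derived from the documents. Because the analysis is exploratory and the 6-month ANCOVA is untouched, the trial's main conclusions do not depend on it.

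**What to change.** Add one sentence to SAP D.7: in the growth-curve analysis, the baseline outcome score is excluded from the covariates and kept as the first of the six outcome points. Leave the covariate list unchanged for the ANCOVA and logistic models.

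The alternative is to keep baseline as a covariate and start the outcome series after baseline. The statements on six time points and on the intercept reflecting baseline status would then also have to be revised. The first option is simpler and had the smaller bias in simulation.

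Either way the cost is a wording change. No data collection, sample size or other analysis is affected.
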